#### **Rationale:**

Venous leg ulcers (VLU) have been reported to affect 0.06-2% of the population. They are known to cause significant physical and psychological disability.

VLU can be caused by reflux within the superficial venous system, by reflux and/or obstruction of the deep venous system, or a combination of these. A key component of the treatment of VLU is compression therapy, which has received a level 1A recommendation in the current SVS guidelines.

The EVRA trial showed that early ablation of superficial venous reflux plays a positive role in increasing the number of patients who reached complete ulcer healing and reduced the time to ulcer healing. There have been a number of publications describing the successful use of foam sclerotherapy to obliterate the refluxing network of veins in the vicinity of the VLU or underlying the VLU. However, it has not previously been shown whether the addition of this technique to the obliteration of superficial venous reflux, the latter being the focus of the EVRA trial, impacts upon VLU healing.

Furthermore, there is no consensus on how to treat VLU associated with post-thrombotic deep venous system reflux or obstruction. Many authors have reported on the beneficial use of foam sclerotherapy to treat VLU in cohort studies. There has been only one randomized study comparing compression alone versus compression and foam sclerotherapy for the treatment of VLU. The authors of this study concluded that it failed to recruit a sufficient number of patients for meaningful comparison (total number of recruited patients was 40).

Therefore, we recognize the need to conduct a prospective randomized study to assess the effect on VLU healing of foam sclerotherapy of the network of veins in the vicinity of the ulcer as an adjunct to obliteration of superficial venous reflux in primary superficial venous reflux patients, and as an adjunct to compression in post-thrombotic patients.

This study will include patients with open VLU caused by primary superficial venous reflux or post-thrombotic deep venous disease.

For the purpose of this study, the refluxing network of veins in the vicinity of the ulcer or underlying the ulcer bed will be termed "ulcer veins". These are to be distinguished from pathological incompetent perforators in the vicinity of the ulcer.

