#### **Objectives:**

- Primary objective:
  - To assess the effect of foam sclerotherapy of the ulcer veins on time to complete VLU healing

- Secondary objectives:
  - o To chart the rate of ulcer healing at 3, 6, 9 and 12 months
  - o To assess the rate of ulcer recurrence
  - To determine the length of time free from ulcers (ulcer-free time) during the first year after randomization
  - o To report health-related quality of life
  - o To describe the side-effects and complications of foam sclerotherapy

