## **Methods:**

- Patients with open venous ulcers (C6) will be assessed by duplex ultrasound scan for
  - o Superficial venous reflux, and identify its source
  - o Evidence of post-thrombotic reflux and/or obstruction, and characterize this
  - o Evidence of refluxing "ulcer veins" and/or pathologic incompetent perforators in the vicinity of the VLU

- Cross sectional or invasive venography +/- intravascular ultrasound at the discretion of the treating physician, based the upon suspicion of proximal venous outflow obstruction
- Patients with open VLU and/or refluxing ulcer veins and/or pathologic incompetent perforators will be eligible for admission to the study
- Individuals meeting inclusion criteria will be offered a participant information sheet
- Written informed consent will be obtained
- Consented patients will be randomized into two groups:
  - o Group A: Foam sclerotherapy for ulcer veins in addition to appropriate therapy
  - o Group B: Appropriate therapy alone without foam sclerotherapy for ulcer veins
- Appropriate therapy:
  - Superficial venous pathology only: will be treated by ablation of the superficial venous reflux by surgery or endovenous techniques, in addition to treatment of incompetent leg tributaries by phlebectomy or foam sclerotherapy.
  - O Superficial venous reflux associated with deep venous obstruction or reflux: treatment of the superficial venous reflux will be individualized and left to the discretion of the vascular surgeon in charge.
  - Deep venous obstruction and / or reflux: patients with iliac vein obstruction may be considered for iliac vein stenting. Otherwise, patients with deep venous pathology will be treated by compression.
- In all participants, the VLU will be debrided as clinically indicated and, if there is evidence of infection, a course of antibiotics will be prescribed according to the local standard of care
- Compression therapy will be provided by trained personnel according to the local standard of
  care. Multilayer elastic compression (two to four layers), short-stretch compression,
  compression stockings, and adjustable compression wraps are all deemed to be acceptable.
   Details of compression types used will be recorded

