#### **Documentation:**

- A secure cloud based digital platform will be created
- Upon randomization, the following data will be collected for each participant:
  - o Unique participant number
  - o **Initial visit clinical assessment:** date, age, gender, clinical center, ulcer size in 2 dimensions, ulcer size as measured by Lesionmeter software, ulcer depth (subjective), ulcer location, ulcer side (right or left lower limb), ulcer duration, presence of pedal pulses, ABPI, history of DVT(s), history of venous intervention(s), type of venous intervention (surgery, ablation, foam, stent), date(s) of venous intervention(s), history of diabetes, HbA1C, BMI (weight and height), cardiac failure (including ejection fraction and NYHA classification), other co-morbidities
  - o **Dressings and compression:** type of ulcer dressing and type of compression used; both recorded at each visit
  - Duplex ultrasound findings: details of superficial and deep system reflux and obstruction
  - o **Foam sclerotherapy:** drug used, concentration, gas used, number of injections, foam volumes injected, number of foam sclerotherapy sessions, perforator treatment
  - Follow up visits: date, ulcer healed?, ulcer size in 2 dimensions, ulcer size as measured by Lesionmeter software, ulcer depth (subjective), foam side effects/complications
  - o **Final visit:** ulcer healed?, ulcer size in 2 dimensions, ulcer size as measured by Lesionmeter software, ulcer depth (subjective), foam side effects/complications
  - **Telephone follow up:** date of date, date of recurrence if any, compliance with compression hosiery
  - o **Ulcer photography:** at least one ulcer photograph at the first visit, and one ulcer or ulcer site photograph during the last visit

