#### Statistical and health economic analysis:

A comprehensive statistical analysis plan will be produced by the study statistician Kaplan-Mayer curves will be created for both Group A and Group B, and will be compared for significance

The total number of patients who achieved complete healing in both groups will be compared Analysis of variance or logistic regression analysis could be used to assess the effect of each variable on healing (age, gender, DM, BMI, ulcer size, and method of treatment)

A health economist will support a health economic evaluation of the study results

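### Allocation and the main comparison ignore disease type, although the rationale asks about foam in two populations with different background treatment

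*Protocol*

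**What the plan says.** The Rationale states that "This study will include patients with open VLU caused by primary superficial venous reflux or post-thrombotic deep venous disease". It frames the question in two parts, with foam as an addition to obliteration of "superficial venous reflux in primary superficial venous reflux patients, and as an adjunct to compression in post-thrombotic patients".

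The Methods tie background treatment to disease type:

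- Superficial disease only: "will be treated by ablation of the superficial venous reflux by surgery or endovenous techniques", with treatment of tributaries.
- Superficial reflux with deep disease: "treatment of the superficial venous reflux will be individualized and left to the discretion of the vascular surgeon in charge".
- Deep disease: compression, with stenting a possibility for iliac obstruction.

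On allocation the Methods say "Consented patients will be randomized into two groups", and no stratification factor is named. The primary objective is a single overall effect: "To assess the effect of foam sclerotherapy of the ulcer veins on time to complete VLU healing". The Sample size section sizes one comparison.

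The Statistical and health economic analysis section compares the healing curves of Groups A and B once. It adds that analysis of variance or logistic regression could be used to look at "age, gender, DM, BMI, ulcer size, and method of treatment". Disease type and ulcer duration are not in that list. Both are available: the Methods place the duplex scan before consent, and the Documentation section lists duplex findings, DVT history and ulcer duration under "Upon randomization, the following data will be collected for each participant". The analysis section also announces a separate SAP, which is not at hand.

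**The concern.** Disease type decides which background treatment a patient receives, so it is a natural candidate for a strong predictor of healing time. With simple allocation, the two arms can differ by chance in their mix of disease types, and an unstratified comparison leaves that variation in the error term. A single pooled estimate also says nothing about whether foam helps on top of ablation, on top of compression, or both, which is how the Rationale poses the question.

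The allocation part is pressing because of timing. An SAP can add covariates or a stratified test later, but it cannot stratify a randomisation that has already been carried out.

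**Working it through.** **Inputs.** From Sample size calculations: mean healing time 75.4 days with compression only; 64.1 days after a 15% effect, so a difference of 11.3 days; SD 39.4 (worst case) or 26; power 90%, alpha 5%; targets of 300 (paired with SD 39.4) or 130 (paired with SD 26). Assumed, because the protocol does not state them: two-sided test, 1:1 allocation, 300 and 130 as trial totals, disease-type shares from 50/50 to 80/20, and a gap D of 10 to 30 days in mean healing time between types.

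**Reproducing the plan's figures.** n per arm = 2 × [SD × (1.96 + 1.2816) / difference]².

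- SD 39.4, difference 11.3: 256 (stated 255).
- SD 26, difference 11.3: 112 (stated 112).
- SD 39.4, difference 75.4 − 47.3 = 28.1: 42 (stated 42).

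These match only as per-arm numbers. That is a separate matter, but it means the pooled comparison has about 70% power with 300 patients at SD 39.4, or 130 at SD 26, before any dropout.

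**Precision.** Share of variance explained by disease type = f(1 − f)D² / SD², taking the SD as that of a mixed population.

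- SD 39.4, 80/20, D = 10: 0.16 × 100 / 1552.4 = 0.010.
- SD 39.4, 50/50, D = 30: 0.25 × 900 / 1552.4 = 0.145.
- SD 26, same two corners: 16 / 676 = 0.024 and 225 / 676 = 0.333.

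At SD 39.4, adjusting for disease type would lower the required number per arm from 256 to between 253 and 219.

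**Chance imbalance.** The 95% limit for the between-arm difference in share is 1.96 × √(2 × 0.25 / n per arm) at a 50/50 mix. Multiplying by D gives the shift in days.

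| Total | Imbalance | Shift, D = 10 | Shift, D = 30 | As share of 11.3 days |
|---|---|---|---|---|
| 300 | ±11.3 points | 1.1 days | 3.4 days | 10% to 30% |
| 130 | ±17.2 points | 1.7 days | 5.2 days | 15% to 46% |

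At 80/20 the shifts are one fifth smaller, since √(0.16 / 0.25) = 0.8.

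This is not a second harm on top of the precision loss. With 300 patients the 95% half-width of the pooled difference is 1.96 × 39.4 × √(2/150) = 8.9 days, and (3.4 / 8.9)² ≈ 0.145, the same 15%.

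**What each half can show.** Normal approximation, difference 11.3 days, all patients evaluable.

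- 300 with SD 39.4, 50/50: 75 per arm in each type, SE = 39.4 × √(2/75) = 6.43, power 42%.
- 300 with SD 39.4, 80/20: 120 and 30 per arm, power 60% and 20%.
- 130 with SD 26: the same to the nearest percent (42%; 60% and 20%).
- Interaction, if the effect exists in one type only: for 300 with SD 39.4, SE = 39.4 × √(4/150 + 4/150) = 9.10 at 50/50, power 24%; at 80/20, 17%. For 130 with SD 26, also 24% and 17%.
- Most favourable cross-pairing, 300 with SD 26: 76% at 50/50, 92% and 39% at 80/20; interaction 33% to 47%.

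**The case against.** The other side has several sound points.

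- **The protocol does not show the size.** A reader might take the 28.1 days between 75.4 and 47.3 as the gap between disease types and conclude that disease type moves healing by more than twice the target effect. The documents do not support that. Those means contrast compression only with compression plus intervention, and no healing time is given by disease type. Nor does the protocol say which populations produced the two SDs. If they were mixed, the between-type variance is already inside them. This stands, and it is why the sizes above rest on an assumed range.
- **Randomising an add-on over varied background care is legitimate.** It gives an unbiased average effect, and the primary objective asks for exactly that. Chance imbalance is random error that the unadjusted test already allows for. This stands: a reading that the result would be biased, or that the trial cannot address its question, goes too far. Within-type estimates remain possible from the data collected.
- **Covariates are commonly left to the SAP.** This stands for the model details. The listed variables are only ones that could be used, and the treatment-method item may simply mean the randomised arm. If it means background treatment, it partly captures disease type. It would then also include discretionary choices that, with no blinding described, may follow knowledge of the allocation. It does not stand for allocation, which is a design feature.
- **Stratifying will not power each half.** True, as the working shows. It is a reason to label the within-type results correctly, not a reason to leave them out.

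**Conclusion.** The point holds as a design weakness, not an error of validity. The Rationale's two-part question is matched by one objective, one sizing and one pooled comparison, with allocation that ignores the factor governing background treatment.

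On the assumed gap of 10 to 30 days and shares of 50/50 to 80/20, the precision at stake is 1% to 15% of the variance at SD 39.4, and 2% to 33% at SD 26. That is small at the low end and material at the high end. In a log-rank or Cox analysis, leaving out a prognostic factor acts mainly by pulling the hazard ratio towards 1 and costing power. The figures in days are therefore a guide on the scale that the protocol used for sizing.

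Under the protocol's own pairings of target and SD, within-type power is about 20% to 60% and interaction power 17% to 24%. The trial is not sized or structured to answer each part separately, and this should be said plainly. The change is worth making because it is nearly free and its main part cannot be made after randomisation starts.

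**What to change.** **Methods.** Stratify randomisation by disease type, classified from the entry duplex and recorded before allocation. The Documentation section now ties data collection to the moment of randomisation, so the order needs stating. Say which stratum takes superficial reflux with deep disease, or use three strata.

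**Statistical and health economic analysis, or the SAP if it does not already do this.** Stratify the log-rank or Cox comparison by disease type and adjust for baseline ulcer size and ulcer duration. Report the foam effect within each disease type with a confidence interval, and an interaction estimate, labelled as estimation only in view of the power above. Define the treatment-method item as the allocated arm, so that background treatment chosen after allocation is not adjusted for.

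**Cost.** One stratification factor in the randomisation list and slightly more analysis. No extra patients are needed for the pooled comparison, and all the variables are already collected. Powering each disease type separately at 90% would be a different trial: 2 × 512 = 1024 evaluable patients at SD 39.4, or 2 × 224 = 448 at SD 26. That is not proposed here.

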#### **Objectives:**

- Primary objective:
  - To assess the effect of foam sclerotherapy of the ulcer veins on time to complete VLU healing

- Secondary objectives:
  - o To chart the rate of ulcer healing at 3, 6, 9 and 12 months
  - o To assess the rate of ulcer recurrence
  - To determine the length of time free from ulcers (ulcer-free time) during the first year after randomization
  - o To report health-related quality of life
  - o To describe the side-effects and complications of foam sclerotherapy

### **Inclusion criteria:**

- Patients with active venous leg ulceration, classified as C6 in the CEAP classification, who have duplex or venography criteria of primary superficial venous reflux, or criteria of post-thrombotic deep venous reflux and/or obstruction, and who show a refluxing network of veins in the vicinity of the ulcer; "ulcer veins", and/or pathologic incompetent perforators.
- Age >18 years

#### **Exclusion criteria:**

- Pregnant and lactating females
- Age <18 years
- Peripheral arterial disease confirmed by ABPI <0.8, or a duplex scan showing significant peripheral arterial disease
- Do not show evidence of a refluxing network of veins in the vicinity of the ulcer; "ulcer veins"
- VLU >2 years duration
- VLU size >20cm in any dimension
- Participant unable to give informed consent

#### **End points:**

- Complete VLU healing at 3, 6, 9 and 12 months from the time of randomization
- Rate of ulcer healing as measured by the reduction in ulcer size during the study period
- Time free from ulcers (ulcer free time) during the 12-month period after randomization
- VLU recurrence during the study period (12 months)

#### **Study design:**

Prospective randomized controlled study

## **Ethics committee approval:**

Pending

## **Methods:**

- Patients with open venous ulcers (C6) will be assessed by duplex ultrasound scan for
  - o Superficial venous reflux, and identify its source
  - o Evidence of post-thrombotic reflux and/or obstruction, and characterize this
  - o Evidence of refluxing "ulcer veins" and/or pathologic incompetent perforators in the vicinity of the VLU

- Cross sectional or invasive venography +/- intravascular ultrasound at the discretion of the treating physician, based the upon suspicion of proximal venous outflow obstruction
- Patients with open VLU and/or refluxing ulcer veins and/or pathologic incompetent perforators will be eligible for admission to the study
- Individuals meeting inclusion criteria will be offered a participant information sheet
- Written informed consent will be obtained
- Consented patients will be randomized into two groups:
  - o Group A: Foam sclerotherapy for ulcer veins in addition to appropriate therapy
  - o Group B: Appropriate therapy alone without foam sclerotherapy for ulcer veins
- Appropriate therapy:
  - Superficial venous pathology only: will be treated by ablation of the superficial venous reflux by surgery or endovenous techniques, in addition to treatment of incompetent leg tributaries by phlebectomy or foam sclerotherapy.
  - O Superficial venous reflux associated with deep venous obstruction or reflux: treatment of the superficial venous reflux will be individualized and left to the discretion of the vascular surgeon in charge.
  - Deep venous obstruction and / or reflux: patients with iliac vein obstruction may be considered for iliac vein stenting. Otherwise, patients with deep venous pathology will be treated by compression.
- In all participants, the VLU will be debrided as clinically indicated and, if there is evidence of infection, a course of antibiotics will be prescribed according to the local standard of care
- Compression therapy will be provided by trained personnel according to the local standard of
  care. Multilayer elastic compression (two to four layers), short-stretch compression,
  compression stockings, and adjustable compression wraps are all deemed to be acceptable.
   Details of compression types used will be recorded
- Foam sclerotherapy: ulcer veins are identified using a linear US probe 7-10Mhz; polidocanol 0.5-1% mixed with gas in a ratio of 1:4 is used to fill the network of refluxing ulcer veins. A total volume of 5-10ml of foam is used per session. Patients are reviewed after 1 week. Foam sclerotherapy may be repeated after one week if the ulcer veins remain patent and the ulcer is not healed. Only two sessions are permitted per lower limb. Following foam sclerotherapy, foam compression is applied
- Ulcer dressing and re-application of compression is performed on a weekly basis until the ulcer is healed
- Following ulcer healing, grade II compression stockings or adjustable compression wraps are prescribed
- After complete healing the patient is followed up monthly by telephone to enquire about ulcer recurrence, and compliance with compression hosiery
- At completion of the study, the patient is reviewed in person

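### The protocol's eligibility rules conflict on patients with an open C6 ulcer and incompetent perforators but no ulcer veins, the only stated target of the randomised foam

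*Protocol*

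**What the plan says.** Three parts of the protocol set entry rules.

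- **Inclusion criteria.** The entry begins "Patients with active venous leg ulceration, classified as C6 in the CEAP classification". It then asks for superficial reflux or post-thrombotic deep disease, and for ulcer veins "and/or pathologic incompetent perforators".
- **Exclusion criteria.** Patients are excluded if they "Do not show evidence of a refluxing network of veins in the vicinity of the ulcer". Perforators are not offered as an alternative here.
- **Methods, eligibility bullet.** Open ulcer is linked by an underlined *and/or* to "refluxing ulcer veins and/or pathologic incompetent perforators will be eligible for admission to the study".

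Two other places fix what these terms mean for the trial. The Rationale defines ulcer veins and adds: "These are to be distinguished from pathological incompetent perforators in the vicinity of the ulcer". Methods defines the randomised contrast as "Group A: Foam sclerotherapy for ulcer veins in addition to appropriate therapy", against appropriate therapy without that foam. The foam bullet later in Methods describes filling the refluxing ulcer veins and names no other target. The primary objective is the effect of that treatment on time to complete healing.

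**The concern.** Eligibility should give one answer for each patient. Here a patient with an open ulcer and incompetent perforators but no ulcer veins qualifies under two statements and is barred by a third. Because the Rationale separates perforators from ulcer veins, the conflict cannot be removed by counting a perforator as an ulcer vein.

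This matters because the arms are defined by foam to ulcer veins. A patient without them has nothing to inject under the treatment as written. Randomising such patients would pull the estimated difference in healing time towards zero. Centres relying on different parts of the protocol would also enrol different populations.

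The Methods bullet has a second, lesser fault. Its chain of *and/or* makes any single item sufficient if taken word for word.

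**Working it through.** **Step 1. Apply each rule to each type of patient** (all other criteria assumed met).

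| Patient | Inclusion criteria | Exclusion criteria | Methods eligibility bullet, taken literally |
|---|---|---|---|
| Open C6 ulcer, ulcer veins present | in | not excluded | in |
| (a) Open C6 ulcer, perforators only | in | out | in |
| (b) Open C6 ulcer, neither finding | out | out | in |
| (c) Ulcer veins or perforators, no open ulcer | out | no bar for lack of an open ulcer as such | in |

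The three rules agree only on the first row. On (a) the formal criteria contradict each other. On (b) and (c) only the Methods bullet departs from the rest.

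**Step 2. Reproduce the plan's own sample sizes.** The inputs are from Sample size calculations: power 90%, alpha 5%, control mean 75.4 days, intervention mean 64.1 days, SD 39.4 or 26. The difference is 75.4 − 64.1 = 11.3 days. I assume a two-sided test and 1:1 allocation, neither of which is stated there.

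n per arm = 2 × (1.96 + 1.2816)² × SD² / difference², where 2 × (3.2416)² ≈ 21.015.

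- SD 39.4: 21.015 × 1552.36 / 127.69 ≈ 255.5, so 256 (protocol: 255).
- SD 26: 21.015 × 676 / 127.69 ≈ 111.3, so 112 (protocol: 112).
- The 28.1-day difference with SD 39.4: 21.015 × 1552.36 / 789.61 ≈ 41.3, so 42 (protocol: 42).

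The figures reproduce as numbers *per arm*. A one-sided test gives 209, 91 and 34 and does not match.

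**Step 3. Illustrate dilution.** Let q be the share of randomised patients without ulcer veins. The documents do not give it, so it is varied. Assume no effect in these patients and an unchanged SD. The average difference becomes 11.3 × (1 − q), and the required size grows by 1/(1 − q)². Starting from 90% power,

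power = Φ((1 − q) × 3.2416 − 1.96).

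| q | Difference (days) | Factor on n | n per arm, SD 39.4 | n per arm, SD 26 | Power |
|---|---|---|---|---|---|
| 0 | 11.30 | 1.00 | 256 | 112 | 90% |
| 10% | 10.17 | 1.23 | 316 | 138 | about 83% |
| 20% | 9.04 | 1.56 | 400 | 174 | about 74% |
| 30% | 7.91 | 2.04 | 522 | 228 | about 62% |

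The power column holds for either SD, taking 255 or 112 patients per arm as the starting size.

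**The case against.** The best defence is that eligibility criteria are applied together. On that reading the exclusion bars every patient without ulcer veins, and no ineligible patient is randomised. This is how criteria normally work, and it limits the point: the risk lies in a centre following the Inclusion criteria or the Methods bullet without the exclusion. It does not remove the conflict. It would leave the perforator alternative in the Inclusion criteria without function, and the consent step in Methods refers only to inclusion: "Individuals meeting inclusion criteria will be offered a participant information sheet".

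Three stronger readings are tempting, but the documents do not support them.

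- *Patients with no open ulcer can be randomised.* Only the literal *and/or* in one Methods bullet suggests this. The first bullet of the same section reads "Patients with open venous ulcers (C6) will be assessed by duplex ultrasound scan for", the Inclusion criteria require C6, the Rationale limits the study to open ulcers, and Methods provides for ulcer debridement in every participant. An open ulcer is clearly intended, and the bullet is a drafting slip.
- *Patients without ulcer veins would certainly receive the same care in both arms.* The foam instructions point that way. However, the Documentation section lists perforator treatment among the foam sclerotherapy data items and does not say in which arm it may be given. Identical care is therefore likely on the text but not established.
- *This trial's power is 83%, 74% or 62%.* Those values start from 90%. The sizes 255 and 112 reproduce per arm, while the targets of 300 and 130 patients read as totals, so the stated targets may not deliver 90% in the first place. That is a separate matter, but it prevents the table from being read as the trial's actual power.

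**Conclusion.** The protocol is wrong as written on one defined group. For an open C6 ulcer with incompetent perforators and no ulcer veins, the Inclusion criteria and the Methods bullet admit and the Exclusion criteria exclude. This conclusion is textual and needs no assumption. The loose wording of the Methods bullet is a secondary fault.

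The size of the consequence is unknown. It depends on how many such patients would be enrolled and on whether foam has any effect in them. The illustrated loss of roughly 7, 16 and 28 percentage points from a nominal 90% treats them as gaining nothing. It shows why the wording matters and is not an estimate for this trial.

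**What to change.** Before enrolment, put one eligibility rule in the Inclusion criteria, the Exclusion criteria and the Methods bullet. In Methods, replace the first *and/or* by *and*, so that an open C6 ulcer is required together with the qualifying vein finding.

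The rule that fits the Rationale, the primary objective, the existing exclusion and the randomised contrast is an open C6 ulcer **and** duplex-proven ulcer veins. Perforators would then be recorded at baseline and would not be an alternative route of entry, so the perforator alternative would come out of both the Inclusion criteria and the Methods bullet.

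If the sponsor intends perforator-only patients to enter, the exclusion has to be changed instead. The protocol must then state what differs between Groups A and B for these patients, in line with the perforator treatment item under Documentation. That choice is the sponsor's.

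The cost is protocol wording. Under the first option recruitment may be slightly slower, although the existing exclusion already rules these patients out.

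### Ablation in mixed disease and iliac stenting are left to discretion, with no requirement to choose before allocation is known and no listed field to record them during the trial

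*Protocol*

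**What the plan says.** The Methods section of the protocol randomises patients to foam sclerotherapy of the ulcer veins plus appropriate therapy (Group A) or to the same background care without it: "Group B: Appropriate therapy alone without foam sclerotherapy for ulcer veins".

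It then defines appropriate therapy by type of disease:

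- **Superficial disease only:** ablation is fixed and only the technique is open.
- **Superficial reflux with deep obstruction or reflux:** "treatment of the superficial venous reflux will be individualized and left to the discretion of the vascular surgeon in charge".
- **Deep disease:** "patients with iliac vein obstruction may be considered for iliac vein stenting"; otherwise the treatment is compression.

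The steps are listed as assessment, consent, randomisation, then treatment. No step between consent and randomisation fixes the background procedure, and no sham procedure or blinding is described anywhere in the protocol.

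The Documentation section places venous procedures in the initial-visit block: "history of venous intervention(s), type of venous intervention (surgery, ablation, foam, stent), date(s) of venous intervention(s". The follow-up entry begins "Follow up visits: date, ulcer healed?, ulcer size in 2 dimensions" and continues with software-measured size, depth and foam side effects. Dressing and compression type are recorded at every visit, and there is a block for foam details and perforator treatment. No entry covers an ablation or a stent carried out after randomisation.

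**The concern.** The primary objective is the effect of foam on time to complete healing. The comparison of arms isolates foam only if the rest of the care does not depend on the arm. In these two strata a surgeon who can know the allocation also chooses a procedure that may itself affect healing. The Rationale says of superficial reflux that "early ablation of superficial venous reflux plays a positive role in increasing the number of patients who reached complete ulcer healing", and adds that it shortened the time to healing.

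A surgeon may be readier to ablate or stent a patient who will not receive foam, which would hide a foam effect. The opposite pattern would flatter foam. Either way the difference would enter the Kaplan-Meier comparison, in which "curves will be created for both Group A and Group B, and will be compared for significance", as if foam had caused it.

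A statistical analysis plan could not repair this afterwards. It cannot recover procedures that were never recorded. Adjusting for a procedure chosen after allocation conditions on a post-randomisation variable.

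**Working it through.** **Text check.** The protocol states no figure on this point, so there is none to reproduce. Three questions decide it.

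1. *Is the choice open?* Yes, in two strata: superficial reflux in mixed disease, and stenting for iliac obstruction. It is not open for superficial disease alone, where ablation is prescribed.
2. *Must the choice precede knowledge of the arm?* No. Duplex and any venography come before consent, so the information is available early, but no sentence requires a decision at that stage.
3. *Would an imbalance show in the listed data?* No. Intervention type and date appear only as history at the initial visit. The later fields cover dressings, compression, foam, perforator treatment, ulcer status, foam side effects, recurrence and compliance with hosiery.

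**Illustration of size.** The protocol gives neither the benefit of these procedures in these strata, nor the share of patients affected, nor the likely difference in use. All three are assumptions:

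- Benefit: 75.4 − 64.1 = 11.3 days. This is the difference the Sample size section plans for, borrowed here.
- Share of patients in the two strata: 25%, 50% or 75%.
- Difference between arms in use within those strata: 10, 20 or 30 percentage points.
- 300 patients read as the trial total (150 per arm), SD 39.4 days, no true foam effect.

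Formulas:

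- Shift = benefit × share × difference in use
- SE = 39.4 × √(2/150) = 4.55 days
- z = shift / SE
- Two-sided type I error = 1 − Φ(1.96 − z) + Φ(−1.96 − z)

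| Share | Difference in use | Shift (days) | Shift as % of 11.3 | z | Type I error |
|---|---|---|---|---|---|
| 25% | 10 points | 11.3 × 0.25 × 0.10 = 0.28 | 2.5% | 0.06 | 5.04% |
| 50% | 20 points | 11.3 × 0.50 × 0.20 = 1.13 | 10% | 0.25 | 5.71% |
| 75% | 30 points | 11.3 × 0.75 × 0.30 = 2.54 | 22.5% | 0.56 | 8.65% |

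**Sensitivity to the sample size.** The Sample size section does not say whether 300 is a total or a number per arm. At 300 per arm, SE = 39.4 × √(2/300) = 3.22 days and the middle case gives 6.4%. With that section's other target, 130 in total with SD 26, SE = 26 × √(2/65) = 4.56 days and the middle case is again 5.7%.

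**Check on the time-to-event scale.** Middle case, 40,000 simulated trials with 150 per arm. Healing times were Weibull with mean 75.4 and SD 39.4 days (shape 2.00), co-treated patients had mean 64.1 days, and follow-up was censored at 365 days. With the procedures used in 60% versus 40% of the affected patients, the log-rank test rejected in 5.9% of trials, against 4.9% with no imbalance.

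**The case against.** **Individualised care is legitimate.** The Rationale says that "there is no consensus on how to treat VLU associated with post-thrombotic deep venous system reflux or obstruction", and the protocol leaves open little beyond what it regards as unsettled. This stands. A reader might infer that the discretion is itself an error, and the document does not support that. The gap is that the choice need not be made before the arm is known.

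**No bias has been shown.** This also stands. The Rationale's statement on ablation is not specific to mixed deep disease, and the protocol gives no healing benefit for iliac stenting. A reader might infer that the trial is biased, or biased in favour of foam. The protocol supports neither reading: it permits choices that depend on the arm, but does not say they will occur or in which direction.

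**The effect is small.** In the middle case it is. The upper case needs a large share, a large systematic difference in use and the full borrowed benefit all at once.

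**The field list is an outline.** It describes a data platform still to be built, and sites might enter trial procedures under the history field. That is possible, so one cannot conclude that they will certainly go unrecorded. But nothing tells sites to do so, whereas dressings and compression are explicitly required at each visit.

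**Conclusion.** The point holds as a cheap improvement and not as a fatal flaw. In two strata the protocol lets a surgeon who may know the arm choose co-treatment that can affect the primary outcome, and it lists no data with which to detect a difference.

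Neither size nor direction can be derived from the document. Under the stated middle-case assumptions the shift is about 1 day and the type I error about 6% instead of 5%. Across the assumed range with 300 patients in total, the shift is 0.3 to 2.5 days and the type I error 5.0% to 8.65%. All of this rests on a borrowed benefit, an assumed share and an assumed imbalance. The shift is zero if use is equal in the two arms or the procedures have no benefit. The case for acting is the low cost of the remedy together with the fact that unrecorded procedures cannot be reliably recovered later.

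**What to change.** In the Methods section, under appropriate therapy, add for patients with deep venous disease: *Before the allocation is opened, the surgeon records the intended background venous procedure (none, superficial ablation, iliac stent, or other, specified). This plan is followed in either arm unless a clinical reason for changing it is documented with its date.*

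In the Documentation section, add to the follow-up and final-visit lists the type and date of every venous procedure done since the last visit, in both arms.

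The declared plan is then fixed before randomisation and can be used as a baseline covariate. The procedure log lets actual use be reported by arm.

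The cost is two extra data fields, with no added visit and no change to the sample size. The surgeon still chooses the procedure, but earlier, and must justify a later change. An unblinded surgeon can still depart from the plan for a documented reason, so the bias is reduced and made visible, not removed.
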